We expect that the standard pulmonary TB treatment regimens recommended by the Union² can be optimized by using daily high dose rifampicin during Cat. 1 primo-treatment. For the here proposed pilot study, dosing of rifampicin would be doubled, while standard dose isoniazid, pyrazinamide and ethambutol would be maintained. Management decisions would be made after 2 weeks of intensive phase, based on remaining numbers and decline of TB bacilli on microscopy for AFB [auramine and fluorescein diacetate (FDA) vital staining]. Those with min. 1 log decline in the number of AFB by FDA smear, or already negative, would continue the unaltered regimen. Those not meeting these criteria would be referred for rapid DST by slide DST and/or Xpert MTB/RIF, depending on ease of referral. In case no rifampicin resistance is detected they would continue the optimized Cat. 1 treatment, with further monitoring by smear and rapid DST as per National TB Programme (NTP) indications, i.e. rapid DST in case a smear is positive at 3, 5 or 6 months; those diagnosed with rifampicin resistance at any time and by any technique would be switched immediately to the standard short "Bangladesh" MDR-TB treatment regimen. In the control arm, referral for rapid DST would be based on non-remittance of fever at the end of the second week, otherwise treatment management remains the same. Failures, relapses and other recurrences of the first-line regimen would all undergo rapid DST, and if not found to be rifampicin resistant they would be re-started on the same 6-month Cat. 1. The current Cat. 2 first-line retreatment regimen would no longer be used in the intervention arm.

Intervention and control treatment regimens (Rh: double dose rifampicin)

New cases	
- intervention:	2 HRhZE / 4 HRh
- control:	2 HRZE / 4 HR (Cat. 1 regimen)
Retreatment cases	
- intervention:	2 HRhZE / 4 HRh
- control:	2 SHRZE / 1HRZE / 5 HRE (Cat. 2 regimen)
MDR patients detected at any time	
	4 KHPtoGCEZ / 5 GCEZ (MDR regimen)

The expected benefits from this optimized treatment regimen cascade are:

1. Reduced occurrence of relapse with susceptible bacilli in patients with extensive disease, due to better sterilizing activity while maintaining the same treatment duration. Total absence of relapse with AFB smear at 2 weeks negative or scanty would suggest that shortening of the regimen to 4 months could be tried for fast converters.

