3. STUDY OBJECTIVES

Primary objective:

To compare a high-dose rifampicin standard TB regimen of 6 months duration with standard TB regimen with respect to adverse treatment outcome (relapse, failure, death and default) and toxicity, in TB cases (new or retreatment, pooled) not shown to have initial rifampicin resistance before one of the standard treatment outcomes applies.

Secondary objectives:

1. To assess whether the study regimen also cures low-level rifampicin resistant TB: by comparing and describing adverse treatment outcomes by initial rifampicin mutations (none, low-level, high)
2. To assess the effectiveness of FDA vital staining screening at two weeks of treatment for early switch of non-responding rifampicin resistant TB to MDR-TB treatment, versus clinical evaluation based on fever resolution. The proportions of rifampicin resistant cases started on MDR treatment within the first 2 months of primo-treatment as well as the proportion of initially present resistance never switched to the MDR regimen and not cured will be compared between the two arms.
3. To assess the negative predictive value of conversion at 2 weeks for relapse
4. To estimate the proportion of acquired rifampicin resistance among failures and relapses
5. To compare the predictive value of auramine with FDA staining at 2 weeks to predict unfavourable outcomes

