 - refer for rapid DST if indicated by algorithm; switch to MDR if rifampicin resistant
 - otherwise continue high-dose treatment
 - o **Control arm only:**

- refer for rapid DST if still fever (temperature $\geq 38^{\circ}\text{C}$); switch to MDR if rifampicin resistant
 - Enquire, register adverse effects. Stop all drugs and refer in case of hepatitis suspicion (feeling sick, anorexia, vomiting, jaundice)
- Visit after four weeks V3: intervention + control arm
 - Clinical check, weight, temperature: improved signs and symptoms of TB?
 - Give treatment, record attendance
 - Liver test
 - Enquire, register adverse effects. Stop all drugs and refer in case of hepatitis suspicion (feeling sick, anorexia, vomiting, jaundice)
- Visit after 2 months V4: intervention + control arm
 - Clinical check, weight, temperature: signs and symptoms of TB absent?
 - Give treatment, record attendance
 - Cat. 1: sputum smear for AFB
 - Refer for rapid DST if AFB-positive (auramine and FDA) and clinically poor evolution; switch to MDR treatment if rifampicin resistant
 - Liver test
 - Enquire, register adverse effects. Stop all drugs and refer in case of hepatitis suspicion (feeling sick, anorexia, vomiting, jaundice)
- Visit after 3 months V5: intervention + control arm
 - Clinical check, weight, temperature: signs and symptoms of TB absent?
 - Give treatment, record attendance
 - Sputum smear for AFB: all Cat. 2 and Cat. 1 patients positive at month 2
 - Refer for rapid DST if AFB-positive (auramine and FDA); switch to MDR treatment if rifampicin resistant
 - Enquire, register adverse effects. Stop all drugs and refer in case of hepatitis suspicion (feeling sick, anorexia, vomiting, jaundice)
- Visit after 4 months V6: intervention + control arm
 - Clinical check, weight, temperature: signs and symptoms of TB absent?
 - Give treatment, record attendance
 - Sputum smear for AFB: Cat. 2 positive at month 3 only
 - Refer for rapid DST if AFB-positive; switch to MDR treatment if rifampicin resistant
 - Enquire, register adverse effects. Stop all drugs and refer in case of hepatitis suspicion (feeling sick, anorexia, vomiting, jaundice)
- Visit after 5 months V7: intervention + control arm
 - Clinical check, weight, temperature: signs and symptoms of TB absent?
 - Give treatment, record attendance
 - Sputum smear for AFB: all patients
 - Declare failure if positive and refer for rapid DST if AFB-positive
 - Switch to MDR treatment if rifampicin resistant

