 - Rifampicin sensitive:
 - Control arm: start Cat. 2
 - Intervention: re-start Cat. 1
 - Enquire, register adverse effects. Stop all drugs and refer in case of hepatitis suspicion (feeling sick, anorexia, vomiting, jaundice)
- Visit after 6 months (or 8 months for Cat. 2) V8: intervention + control arm
 - Clinical check, weight, temperature: signs and symptoms of TB absent?
 - Stop treatment, record attendance
 - Sputum smear for AFB: all patients
 - Declare cured if negative and inform about signs of relapse
 - Declare failure if positive and refer for rapid DST if AFB-positive

- Switch to MDR treatment if rifampicin resistant
- Rifampicin sensitive:
 - Control arm: re-register, start Cat. 2
 - Intervention: re-register, re-start Cat. 1
- Enquire, register adverse effects
- Make appointment for check-up after 12 months

- Visit 12 months after end of treatment V9 (intervention + control arm cured or defaulted)

- Reminders, home visit if not attending
- History from relatives / neighbours if not met (retreated or died of TB?)
- Clinical check: signs and symptoms of TB absent?
- If attending at the clinic only: weight, temperature
- Sputum smear and culture for AFB
 - If negative: further passive follow-up
 - If positive: declare relapse and refer for rapid DST
 - Switch to MDR treatment if rifampicin resistant
 - Rifampicin sensitive:
 - Control arm: re-register, start Cat. 2
 - Intervention: re-register, re-start Cat. 1

All enrolled patients will be monitored intensively for drug toxicity (clinical; liver enzymes during the first 2 months). Treatment will be interrupted in case of a serious adverse event, possibly due to the TB drugs, and patients referred to the nearest project hospital. In case of toxic hepatitis, after full recovery drugs will be re-introduced in hospital one by one, aiming at re-starting the same regimen since this toxicity is often transient and probably not rifampicin dose-related.

Unscheduled visits can take place at any time during the patients participation in the study. During these visits, all study procedures will be performed if needed, and data will be collected.

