8.4 Sample size and power

The sample size of two times 500 patients is a trade-off between precision and exposing an excessively high number of patients to potentially more toxic treatment. Power has not been taken into account, but if the results are favourable large scale cluster-randomized study will be designed to bring definitive proof.

The registered incidence of clinically apparent hepatitis from any cause during TB treatment is 1.5% for the study population. With the proposed sample size, an increase by at least 2% compared to the control arm will attain statistical significance ($p=0.047$).

With the standard (=control) regimens and definitions, about 2% failures and 2% relapses are currently notified by the DF project, but only 50% of those are culture-positive, and about half of the culture positive failures and relapses are rifampicin-resistant. Overall cure rate (new and retreatment cases together) is close to 90%, with 4% default and 4% deaths. Based on the data from 2010 about 20 cases with rifampicin resistance may be enrolled, 10 in each arm. We estimate that the more effective study regimen plus early detection of serious drug resistance rolled over to MDR-TB

treatment will prevent drug resistant failure and relapse, reduce rifampicin susceptible relapse to an estimated two third, and reduce death and default because of unrecognized rifampicin resistance to 80% of the control arm. This total estimated reduction of unfavourable outcome from 10% to 7% remains non-significant with the targeted enrolment of two times 500 cases. With 80% power and 95% confidence level, 2 x 1421 patients would have to be enrolled, which is not feasible and also difficult to justify. However, a slightly larger reduction of unfavourable outcome from 10% to 6.5% comparing two arms of 500 cases each would already result in a significant p-value. Additional evidence will be obtained studying *rpoB* mutations, initially (all smear-positives) and at time of failure or relapse (only in the few such cases expected). Absence of low-level resistance mutations only among patients with unfavourable outcome on the high-dose arm, while they were present among new cases in both arms, will be interpreted as additional evidence of effectiveness of the increased dosing.

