## **7. Analysis of secondary objectives**

7.1. To assess whether the study regimen also cures low-level rifampicin resistant TB

The interaction between treatment differences and initial rifampicin resistance mutations detected will be tested in the logistic regression model from the main analysis. Initial rifampicin resistance mutations detected is categorized as:

- None
- Low-level
- High

7.2. To assess the effectiveness of FDA vital staining screening at two weeks of treatment for early switch of non-responding rifampicin resistant TB to MDR-TB treatment, versus clinical evaluation based on fever

The proportions of initial rifampicin resistant cases started on MDR treatment within the first 2 months of primo-treatment as well as the proportion of initially present resistance never switched to the MDR regimen and not cured will be compared between the two arms using the chi-squared or Fisher's exact test.

7.3. To assess the negative predictive value of conversion at 2 weeks for relapse

The complement of the Negative Predictive value (with 95% Wilson CI) of conversion in the intervention arm will be estimated as the % of relapses among those who are already completely negative on AFB smear (auramine or FDA) at week 2.

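### SAP 7.2 sets no time limit on 'never switched', so missed resistance that fails or relapses and is then switched drops out of the harm measure

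*SAP*

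**What the plan says.** Secondary objective 2 asks whether FDA staining at two weeks leads to earlier MDR treatment of resistant patients than a fever check does. SAP 7.2 gives two measures, each to be tested by chi-squared or Fisher's test. The first is "The proportions of initial rifampicin resistant cases started on MDR treatment within the first 2 months of primo-treatment". The second is the harm measure, for which "the proportion of initially present resistance never switched to the MDR regimen and not cured will be compared between the two arms". Protocol section 3, objective 2, defines the same quantity: "the proportion of initially present resistance never switched to the MDR regimen and not cured". Neither document says when a patient stops being at risk of a switch.

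Protocol 1.1 states: "Failures, relapses and other recurrences of the first-line regimen would all undergo rapid DST". Section 5.3 repeats this by visit. At months 5 and 6 (or 8) the instruction is "Declare failure if positive and refer for rapid DST if AFB-positive", and at the 12-month visit it is "If positive: declare relapse and refer for rapid DST". Each is followed by a switch to MDR treatment if the result is resistant. Protocol 5.1 applies the same switch to every patient in whom resistance is detected.

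**The concern.** The second measure is the only one of the two that looks at outcome. It is meant to show what happens to resistant patients whom week-2 screening overlooks. Failure or relapse is a likely course for such a patient, and it is also the event that triggers the test and the switch. Once switched, the patient is no longer 'never switched', so the harm that screening should have prevented removes the patient from the count of harm.

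Protocol 8.4 predicts that the strategy will prevent drug-resistant failure and relapse, and protocol 1.1 describes late switching as the weakness of current practice. The measure may therefore understate the difference that the sponsor expects to see.

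**Working it through.** **1. How each pathway is scored.** All rows are initially resistant patients.

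| Pathway | MDR start within 2 months | Never switched and not cured | Adverse outcome before MDR start |
|---|---|---|---|
| Switched at week 2 | yes | no | no |
| Missed; switched later, before any adverse outcome | no | no | no |
| Missed; fails or relapses, tests resistant, switched | no | **no** | **yes** |
| Missed; fails or relapses, rapid DST negative or missing | no | yes | yes |
| Dies or defaults without a switch | no | yes | yes |
| Cured without a switch | no | **no** | **no** |

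On the two planned measures together, the third row and the last row are identical: a late switch after failure or relapse scores like a cure. The last row may not be empty. Protocol 1.2 says that some low-level resistant disease seems curable on standard regimens, and objective 1 asks whether the high dose cures it.

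**2. Denominator.** Protocol 8.4 expects about 20 resistant patients, 10 per arm. Taking the 2% from the 2010 survey (protocol 1.1) with 1000 enrolled: 0.02 × 1000 = 20, or 10 per arm. The figure reproduces.

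**3. How many could be affected.** Protocol 8.4 gives 2% failures plus 2% relapses, half of them culture-positive, and "about half of the culture positive failures and relapses are rifampicin-resistant". Per arm: 0.04 × 0.5 × 0.5 × 500 = 5. This is an upper bound for initially resistant controls, for two reasons. Some of these events may be acquired resistance, and the rates come from programme care, whereas trial controls also get fever-triggered DST at week 2.

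**4. Cross-check on assumptions.** Protocol 1.2 reports 63% failure or relapse on standard treatment for low-level resistant strains and calls adverse outcomes comparable for high-level ones. Assume that 60–100% of resistant controls and 20–40% of resistant intervention patients are not switched early, and apply 63% in both arms. Events per 10 resistant patients = 10 × share missed × 0.63:

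- control: 3.8 to 6.3
- intervention: 1.3 to 2.5

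The top of the control range needs every resistant control to be missed early. The order of magnitude agrees with step 3.

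**5. What the planned measure counts of these.** Multiply by (1 − sensitivity of the rapid DST at failure or relapse), with sensitivity assumed:

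| Sensitivity | Control | Intervention |
|---|---|---|
| 100% | 0 | 0 |
| 90% | 0.4–0.6 | 0.1–0.25 |
| 80% | 0.8–1.3 | 0.25–0.5 |

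Adding 8% death or default (the overall rates in protocol 8.4, assumed to apply to missed resistant patients), the redefined measure counts 10 × share missed × 0.71: 4.3 to 7.1 in control and 1.4 to 2.8 in intervention.

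**The case against.** **The measure is not empty.** A reader might infer that missed resistance always scores zero. The documents do not support that. Deaths and defaults without a switch count. The switch depends on a resistant local rapid DST, while the reference laboratory result prevails for analysis (protocol 5.4), and protocol 1.2 reports about 10% extra yield of slide DST over Xpert. Failures and relapses with a negative or missing rapid DST therefore stay in.

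**The measures are paired.** A reader might also infer that SAP 7.2 cannot tell a perfect strategy from one that misses everyone. It can: the 2-month measure would read 100% against 0%. What it cannot do is separate late-switched harm from cure without a switch.

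**Power is a weak argument.** Suppose 5 failures or relapses and 2 deaths or defaults among 10 controls, against 1 and 1 among 10 intervention patients. The planned measure compares 2/10 with 1/10 (Fisher p = 1.0, power 1.2%); counting adverse outcome before switch compares 7/10 with 2/10 (p = 0.070, power 42.6%). But if the remaining 3 and 8 patients were switched early, the 2-month measure compares 3/10 with 8/10, with the same p-value and power as 7/10 with 2/10. The counts are invented, and protocol 8.1 describes a pilot for estimation. The contrast illustrates scoring and nothing more.

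**A narrower reading exists.** 'Never switched' could mean during the first course, and SAP 4.1 does use the outcome after the first regimen for the intention-to-treat analysis. But SAP 7.2 does not invoke that rule, so a clarification is needed even if this was the intent.

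**The events appear elsewhere.** Resistant failures and relapses enter the primary endpoint and the mutation-group analysis in SAP 7.1. This coverage is partial, because SAP 4.2 excludes patients switched before an outcome and the full resistant denominator is lost.

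**Failure and relapse also carry a regimen effect.** This stands. The double dose is itself meant to change them, so the comparison cannot isolate screening. The 'not cured' part of the present measure already has that feature.

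**Conclusion.** The concern holds in a limited form. As written, the second measure for objective 2 leaves out initially resistant patients who are missed at week 2, fail or relapse, and are switched after a resistant rapid DST. Neither the 2-month measure, SAP 7.1 nor the primary endpoint restores that comparison over all initially resistant patients.

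With about 10 such patients per arm, several controls could be affected, up to about 5 if every resistant failure and relapse in protocol 8.4 were initially resistant. The early-miss shares, the DST sensitivities, and the use of 63% and 8% in both arms are assumptions. The objective is secondary and the trial is a pilot, so the consequence is a misleading description of harm; the primary analysis is untouched.

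**What to change.** In SAP 7.2, define the second measure as the proportion of initially rifampicin-resistant patients who had failure, relapse, death or default before MDR treatment was started, over all initially resistant patients in the arm. An equivalent wording is: not switched before a standard outcome of the first treatment course applied, and not cured, with cure followed by relapse counted as relapse as in SAP 4.2.

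Also:

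- State that the SAP 4.2 exclusion of patients switched before an outcome does not apply to this denominator, and how patients who are transferred out, lost, or complete treatment without proof of cure are handled.
- Tabulate by arm: early switch; late switch before any adverse outcome; adverse outcome before switch; cured without switch; and any remainder. Keep 'never switched' as a descriptive row.
- State that the arm comparison reflects regimen and screening together.

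The cost is SAP wording and an aligning edit to protocol section 3, objective 2, handled under the amendment procedure in protocol 11.2. Treatment outcomes and MDR switches are already followed, so no new data or clinical procedure is needed.

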8.3.4 Secondary and tertiary analysis

Secondary Objectives

1. *To assess whether the study regimen also cures low-level rifampicin resistant TB*

Adverse treatment outcomes will be described and compared among treatment groups in subgroups defined by initial rifampicin resistance mutations (performed in all patients) detected:

- none

- low-level
- high

2. *To assess the effectiveness of standard auramine versus FDA vital staining screening at two weeks of treatment for early switch of non-responding rifampicin resistant TB to MDR-TB treatment*

The proportion of initial rifampicin resistant case detected by FDA (i.e. the sensitivity of FDA) will be estimated together with 95% CI. The same analysis will be performed for auramine or ZN AFB smears and compared with FDA. Also the number of referrals needed with both techniques will be compared.

3. *To assess the negative predictive value of conversion at 2 weeks for relapse*

The Negative Predictive value (and 95% CI) of conversion in the intervention arm will be estimated as the % of relapses among those with a minimum 1 log decline in the number of AFB, or who are already negative or only scanty positive on AFB smear (auramine or FDA) at week 2.

4. *To estimate the proportion of acquired rifampicin resistance among failures and relapses*

Proportions will be estimated together with 95% confidence intervals, using the number of failure / relapse cases without mutation detected at diagnosis as the denominator and comparing intervention and control arms.

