#### 4.2. Efficacy study endpoints

##### *Primary endpoint*

The primary efficacy endpoint is the incidence of adverse treatment outcomes. Following the WHO guidelines from 2010, as currently in use in the NTP in Bangladesh, an adverse treatment outcome is defined as any occurrence of the following:

- Relapse: Cured previously from TB or completed treatment for TB and now having bacteriologically positive sputum for TB (at 12 months follow-up or at an earlier time point)
- Default: The patient whose treatment was interrupted for 2 consecutive months or more.

- Failure: Sputum positive for TB at 5 months or later during treatment. Failure will also be declared if the regimen has to be changed for at least 2 drugs due to adverse events.
- Death: All-cause mortality between case registration and end of TB treatment (related or not to TB or TB treatment)

Patients who are transferred out will be excluded from the outcome analysis.

In line with current WHO recommendations, patients detected with MDR-TB or rifampicin resistance before any outcome applies and switched to the MDR-TB regimen will be excluded from the outcome analysis.

Analyses will be performed using the NTP smear-based recurrence (failure, relapse) definitions, but as a secondary approach culture-based definitions will be used. In each analysis, if a patient has two events for the analysis of interest, the first endpoint will be taken into account, except for cured/completed followed by relapse which is considered as relapse.

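### SAP 7.3: the relapse percentage among 2-week converters keeps patients who cannot be relapses in its denominator, and covers only part of the group that the protocol defines

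*SAP*

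**What the plan says.** SAP 7.3 defines one statistic for this objective. "The complement of the Negative Predictive value (with 95% Wilson CI) of conversion in the intervention arm" is the quantity, and it "will be estimated as the % of relapses among those who are already completely negative on AFB smear (auramine or FDA) at week 2". No further condition is placed on the denominator.

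SAP 4.2 decides who can be a relapse: "Cured previously from TB or completed treatment for TB and now having bacteriologically positive sputum for TB", at the 12-month visit or before it. When a patient has two events, "the first endpoint will be taken into account, except for cured/completed followed by relapse which is considered as relapse". The same section takes transfers, and patients switched to the MDR regimen before any outcome applies, out of the outcome analysis. It says that the secondary objectives use these outcome definitions.

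On loss to follow-up, SAP 4.1.1 and 6.2(b) count patients lost before the 12-month visit as adverse outcomes in the intention-to-treat analysis, unless they are known to have left the area. SAP 6.2(b) then adds a general imputation step. Protocol 4.5 says that loss to follow-up for the relapse check will be handled on its own.

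Protocol 8.3.4 (objective 3) has the same form, a percentage of relapses among converters, but a wider group: "those with a minimum 1 log decline in the number of AFB, or who are already negative or only scanty positive on AFB smear", by auramine or FDA. The reason for wanting the figure is in protocol 1.1, which treats a shorter course in fast converters as something to try: "Total absence of relapse with AFB smear at 2 weeks negative or scanty would suggest that shortening of the regimen to 4 months".

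**The concern.** A relapse percentage should rest on patients in whom a relapse could have been recorded. If patients who could never be recorded as relapses stay in the denominator, the percentage can only come out too low and its confidence interval too narrow. Both errors favour the reading that fast converters hardly relapse, which is what the protocol wants to learn about them.

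The definition of conversion raises a second question. The protocol names one group in its analysis section and a narrower one in its argument for shortening. The SAP analyses a third, narrower still, and gives no reason.

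**Working it through.** SAP 7.3 states no figure to reproduce, so the check is of the formula.

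**Who is in the denominator but cannot be in the numerator.** Failures, defaulters and deaths on treatment have a first endpoint that is not relapse, and they were not cured or completed. Protocol 5.3 invites defaulters to the 12-month visit and tells staff to declare relapse on a positive result. Under SAP 4.2, though, such a patient's first endpoint is default.

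**Inputs.**
- Failure 2%, default 4%, death 4% (protocol 8.4, all patients on control regimens), so f = 2% + 4% + 4% = 10%. This fits the cure rate of close to 90% given there.
- Relapse risk r among completers whose status is known: 2% as notified (protocol 8.4), and 6% for extensive disease or HIV co-infection (protocol 1.2).
- Share L of completers not assessed after treatment: not in the documents, assumed from 0% to 30%.

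**Formula.** Percentage shown = r × (1 − f) × (1 − L), if unassessed patients stay in the denominator as non-relapses.

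| L (assumed) | shown if r = 2% | shown if r = 6% | relative shortfall |
|---|---|---|---|
| 0% | 2.0 × 0.90 × 1.00 = 1.80% | 5.40% | 10% |
| 10% | 2.0 × 0.90 × 0.90 = 1.62% | 4.86% | 19% |
| 20% | 2.0 × 0.90 × 0.80 = 1.44% | 4.32% | 28% |
| 30% | 2.0 × 0.90 × 0.70 = 1.26% | 3.78% | 37% |

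Only the first row rests on the documents' own rates. If the notified 2% is already per registered patient, the comparison becomes 2.0% shown against 0.02 / 0.90 = 2.2% among completers, which is the same 10% shortfall.

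**Zero relapses observed.** The 95% Wilson upper limit for 0/n is 3.84 / (n + 3.84). Assume 200 completely negative patients, since the documents give no number:
- all converters, n = 200: 1.88%
- completers, n = 180 (L = 0%): 2.09%
- completers assessed, n = 162 (L = 10%): 2.32%
- completers assessed, n = 144 (L = 20%): 2.60%

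**The missing rule for unassessed completers.** Take the same 200 with L = 10% and no relapse seen. The 18 unassessed completers (200 × 0.90 × 0.10) can be left in as non-relapses (0/200) or left out together with the non-completers (0/162). If the intention-to-treat rule is read as making them events, the result is 18/200 = 9%. The SAP does not choose among these. SAP 7.4, by contrast, does state its denominator.

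**Conversion definitions side by side.**
- SAP 7.3: completely negative.
- Protocol 1.1: negative or scanty.
- Protocol 8.3.4: at least a 1-log decline, or negative, or scanty.

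Each group lies inside the next. The SAP group can be no larger than the one in protocol 1.1, and size matters: with zero relapses the Wilson upper limit is 3.70% at n = 100 and 1.88% at n = 200 (both sizes assumed).

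**Stain.** Auramine or FDA can mean negative on either stain, or one analysis for each. SAP 7.5 compares the stains, but against any adverse outcome and not relapse alone.

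**The case against.** The strongest reply is that this is an inherited and small matter. Protocol 8.3.4 already has the percentage-among-converters form and the auramine-or-FDA wording. The SAP even improves on it by calling the relapse percentage the complement of the predictive value. That is correct, but the SAP is where the denominator should be settled.

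On size, the 10% comes from all patients on control regimens, counted from registration. Week-2 converters on the intervention have survived two weeks and may do better, so their share could be smaller. That stands. Follow-up is also active: protocol 5.3 provides for reminders, home visits and information from relatives or neighbours, so loss may be low.

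A further point is that total absence of relapse is a condition on the numerator. Zero stays zero under any denominator, and only the upper limit moves. Protocol 2.1 also places the question of shortening at the end-of-treatment interim analysis, which excludes relapse, so SAP 7.3 does not feed that decision. Both points stand and limit the consequence.

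Finally, relapse among all patients negative at week 2 is a legitimate quantity, while restricting to assessed completers conditions on later events. That is fair, and a reason to show both, each labelled.

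A reader might also infer four stronger things that the documents do not support:
- That patients switched to the MDR regimen are kept in the denominator. SAP 4.2 excludes them, and transfers, from the outcome analysis, and this probably carries over to the secondary objectives.
- That the SAP counts unexamined patients as relapse-free. It is silent on them.
- That narrowing conversion to completely negative itself lowers the relapse rate. It changes the population, which is a different thing from bias.
- That SAP 2.2 is inaccurate in announcing only an added objective. Objective 3 has the same wording in both documents, and what changed is an analysis definition.

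**Conclusion.** The point holds in a limited form. As written, the denominator in SAP 7.3 includes patients who cannot meet the SAP's own relapse definition, and the direction is understatement. On the documents' figures the size is about 0.2 percentage points (2.0% shown as 1.8%), assuming that the notified 2% is the risk among completers and that control-regimen rates apply to converters. The drop to 1.6% or 1.4% depends on an assumed 10% or 20% loss after treatment.

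It would go too far to say that the protocol's question about fast converters is missed. Completely negative patients are a subset of the negative-or-scanty group, so the question is answered in part, and the scanty patients are never estimated. The primary analysis is not affected. This is a secondary objective in a pilot estimation study, and a change worth making because it is cheap.

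**What to change.** In SAP 7.3:
- Use as denominator the converters who were cured or completed and whose relapse status is known at 12 months, or in whom relapse was ascertained earlier.
- Report the number of cured or completed converters left unassessed, and give the all-converter percentage as a sensitivity analysis. The gap between the two shows how much rests on patients who could not be, or were not, seen to relapse.
- Report FDA and auramine separately.
- For each stain, report completely negative, negative or scanty, and at least a 1-log decline (with negative and scanty counted in, as in protocol 8.3.4). Give the count range that scanty stands for.
- Show the same percentage for non-converters alongside.

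The cost is SAP wording, a few more table rows and a slightly wider confidence interval: for 200 converters without relapse, an upper limit of 2.09% to 2.60% in place of 1.88% at 0% to 20% assumed loss. No new data collection is needed, since the intervention arm already has both stains at enrolment and week 2.
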